5.3.2 Eliciting Adverse Event Information

A consistent methodology of non-directive questioning should be adopted for eliciting adverse event information at all patient evaluation timepoints. Examples of non-directive questions include the following:

"How have you felt since your last clinic visit?"

"Have you had any new or changed health problems since you were last here?"

5.3.3 Assessment of Severity of Adverse Events

The adverse event severity grading scale in [Table 3](#) will be used for assessing adverse event severity.

Table 3 Adverse Event Severity Grading Scale

Severity	Description
Mild	Discomfort noticed, but no disruption of normal daily activity
Moderate	Discomfort sufficient to reduce or affect normal daily activity
Severe	Incapacitating with inability to work or to perform normal daily activity

Note: Regardless of severity, some events may also meet seriousness criteria. Refer to definition of a serious adverse event (see [Section 5.2.2](#)).

5.3.4 Assessment of Causality of Adverse Events

Investigators should use their knowledge of the patient, the circumstances surrounding the event, and an evaluation of any potential alternative causes to determine whether an adverse event is considered to be related to the study drug, indicating "yes" or "no" accordingly. The following guidance should be taken into consideration:

- Temporal relationship of event onset to the initiation of study drug
- Course of the event, with special consideration of the effects of dose reduction, discontinuation of study drug, or reintroduction of study drug (as applicable)
- Known association of the event with the study drug or with similar treatments
- Known association of the event with the disease under study
- Presence of risk factors in the patient or use of concomitant medications known to increase the occurrence of the event
- Presence of non-treatment-related factors that are known to be associated with the occurrence of the event

5.3.5 Procedures for Recording Adverse Events

Investigators should use correct medical terminology/concepts when recording adverse events on the Adverse Event eCRF. Avoid colloquialisms and abbreviations.

For the purposes of reporting events of infection and inflammation of the eye, the following terms and definitions should be used.

- Iritis: the presence of inflammatory cells in the anterior chamber
The presence of aqueous flare alone will not constitute iritis but should be documented as an anterior chamber flare for adverse event reporting purposes.
- Iridocyclitis: the presence of inflammatory cells in both the aqueous and vitreous
- Vitritis: the presence of active inflammation in the vitreous, demonstrated by the presence of inflammatory cells (trace or greater)

Active inflammation in the vitreous should be clinically differentiated from cellular debris from prior episodes of inflammation, hemorrhage, or other causes.

- Endophthalmitis: diffuse intraocular inflammation predominantly involving the vitreous cavity but also involving the anterior chamber, implying a suspected underlying infectious cause

Note: Trace benign, aqueous pigmented cells visible on slitlamp examination that are caused by dilation and are not RBCs or WBCs or the result of any ocular disorder should not be recorded as an adverse event.

Only one adverse event term should be recorded in the event field on the Adverse Event eCRF.

5.3.5.1 Diagnosis versus Signs and Symptoms

A diagnosis (if known) should be recorded on the Adverse Event eCRF rather than individual signs and symptoms (e.g., record only liver failure or hepatitis rather than jaundice, asterixis, and elevated transaminases). However, if a constellation of signs and/or symptoms cannot be medically characterized as a single diagnosis or syndrome at the time of reporting, each individual event should be recorded on the Adverse Event eCRF. If a diagnosis is subsequently established, all previously reported adverse events based on signs and symptoms should be nullified and replaced by one adverse event report based on the single diagnosis, with a starting date that corresponds to the starting date of the first symptom of the eventual diagnosis.

5.3.5.2 Adverse Events That Are Secondary to Other Events

In general, adverse events that are secondary to other events (e.g., cascade events or clinical sequelae) should be identified by their primary cause, with the exception of severe or serious secondary events. A medically significant secondary adverse event that is separated in time from the initiating event should be recorded as an independent event on the Adverse Event eCRF. For example:

- If vomiting results in mild dehydration with no additional treatment in a healthy adult, only vomiting should be reported on the eCRF.
- If vomiting results in severe dehydration, both events should be reported separately on the eCRF.
- If a severe gastrointestinal hemorrhage leads to renal failure, both events should be reported separately on the eCRF.
- If dizziness leads to a fall and consequent fracture, all three events should be reported separately on the eCRF.
- If neutropenia is accompanied by an infection, both events should be reported separately on the eCRF.

All adverse events should be recorded separately on the Adverse Event eCRF if it is unclear as to whether the events are associated.

5.3.5.3 Persistent or Recurrent Adverse Events

A persistent adverse event is one that extends continuously, without resolution, between patient evaluation timepoints. Such events should only be recorded once on the Adverse Event eCRF. The initial severity (intensity or grade) of the event will be recorded at the time the event is first reported. If a persistent adverse event becomes more severe, the most extreme severity should also be recorded on the Adverse Event eCRF. If the event becomes serious, it should be reported to the Sponsor immediately (i.e., no more than 24 hours after learning that the event became serious; see Section 5.4.2 for reporting instructions). The Adverse Event eCRF should be updated by changing the event from "non-serious" to "serious," providing the date that the event became serious, and completing all data fields related to serious adverse events.

A recurrent adverse event is one that resolves between patient evaluation timepoints and subsequently recurs. Each recurrence of an adverse event should be recorded as a separate event on the Adverse Event eCRF.

5.3.5.4 Abnormal Laboratory Values

Not every laboratory abnormality qualifies as an adverse event. A laboratory test result must be reported as an adverse event if it meets any of the following criteria:

- Is accompanied by clinical symptoms
- Results in a change in study treatment (e.g., dosage modification, treatment interruption, or treatment discontinuation)
- Results in a medical intervention (e.g., potassium supplementation for hypokalemia) or a change in concomitant therapy
- Is clinically significant in the investigator's judgment

It is the investigator's responsibility to review all laboratory findings. Medical and scientific judgment should be exercised in deciding whether an isolated laboratory abnormality should be classified as an adverse event.

If a clinically significant laboratory abnormality is a sign of a disease or syndrome (e.g., alkaline phosphatase and bilirubin $5 \times$ the upper limit of normal [ULN] associated with cholestasis), only the diagnosis (i.e., cholestasis) should be recorded on the Adverse Event eCRF.

If a clinically significant laboratory abnormality is not a sign of a disease or syndrome, the abnormality itself should be recorded on the Adverse Event eCRF, along with a descriptor indicating whether the test result is above or below the normal range (e.g., "elevated potassium," as opposed to "abnormal potassium"). If the laboratory abnormality can be characterized by a precise clinical term per standard definitions, the clinical term should be recorded as the adverse event. For example, an elevated serum potassium level of 7.0 mEq/L should be recorded as "hyperkalemia."

Observations of the same clinically significant laboratory abnormality from visit to visit should only be recorded once on the Adverse Event eCRF (see Section 5.3.5.3 for details on recording persistent adverse events).

5.3.5.5 Abnormal Vital Sign Values

Not every vital sign abnormality qualifies as an adverse event. A vital sign result must be reported as an adverse event if it meets any of the following criteria:

- Is accompanied by clinical symptoms
- Results in a change in study treatment (e.g., dosage modification, treatment interruption, or treatment discontinuation)
- Results in a medical intervention or a change in concomitant therapy
- Is clinically significant in the investigator's judgment

It is the investigator's responsibility to review all vital sign findings. Medical and scientific judgment should be exercised in deciding whether an isolated vital sign abnormality should be classified as an adverse event.

If a clinically significant vital sign abnormality is a sign of a disease or syndrome (e.g., high blood pressure), only the diagnosis (i.e., hypertension) should be recorded on the Adverse Event eCRF.

Observations of the same clinically significant vital sign abnormality from visit to visit should only be recorded once on the Adverse Event eCRF (see Section 5.3.5.3 for details on recording persistent adverse events).

5.3.5.6 Abnormal Liver Function Tests

The finding of an elevated ALT or AST ($>3 \times \text{ULN}$) in combination with either an elevated total bilirubin ($>2 \times \text{ULN}$) or clinical jaundice in the absence of cholestasis or other causes of hyperbilirubinemia is considered to be an indicator of severe liver injury (as defined by Hy's law). Therefore, investigators must report as an adverse event the occurrence of either of the following:

- Treatment-emergent ALT or AST $>3 \times \text{ULN}$ in combination with total bilirubin $>2 \times \text{ULN}$
- Treatment-emergent ALT or AST $>3 \times \text{ULN}$ in combination with clinical jaundice

The most appropriate diagnosis or (if a diagnosis cannot be established) the abnormal laboratory values should be recorded on the Adverse Event eCRF (see Section 5.3.5.1) and reported to the Sponsor immediately (i.e., no more than 24 hours after learning of the event), as a serious adverse event or an adverse event of special interest not considered serious (see Section 5.4.2).

5.3.5.7 Deaths

All deaths that occur during the protocol-specified adverse event reporting period (see Section 5.3.1), regardless of relationship to study drug, must be recorded on the Adverse Event eCRF and immediately reported to the Sponsor (see Section 5.4.2).

Death should be considered an outcome and not a distinct event. The event or condition that caused or contributed to the fatal outcome should be recorded as the single medical concept on the Adverse Event eCRF. Generally, only one such event should be reported. If the cause of death is unknown and cannot be ascertained at the time of reporting, "**unexplained death**" should be recorded on the Adverse Event eCRF. If the cause of death later becomes available (e.g., after autopsy), "unexplained death" should be replaced by the established cause of death. *The term "sudden death" should not be used unless combined with the presumed cause of death (e.g., "sudden cardiac death").*

Deaths that occur after the adverse event reporting period should be reported as described in Section 5.6.

5.3.5.8 Preexisting Medical Conditions

A preexisting medical condition is one that is present at the screening visit for this study. Such conditions should be recorded on the Medical History and Baseline Conditions eCRFs.

A preexisting medical condition should be recorded as an adverse event only if the frequency, severity, or character of the condition worsens during the study. When recording such events on the Adverse Event eCRF, it is important to convey the concept that the preexisting condition has changed by including applicable descriptors (e.g., "more frequent headaches").

5.3.5.9 Lack of Efficacy or Worsening of Age-Related Macular Degeneration

Medical occurrences or symptoms of deterioration that are anticipated as part of AMD should be recorded as an adverse event if judged by the investigator to have unexpectedly worsened in severity or frequency or changed in nature at any time during the study. When recording an unanticipated worsening of AMD on the Adverse Event eCRF, it is important to convey the concept that the condition has changed by including applicable descriptors (e.g., "accelerated AMD").

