
 To evaluate the safety of multiple IVT doses of RO6867461 at 12- and 16-week intervals 	
 Incidence and severity of ocular adverse events Incidence and severity of non-ocular adverse events Other safety data, including but not limited to, reasons for withdrawal from study, laboratory data, concomitant medications, vital signs, and physical examination results will be listed and summarized descriptively

Table 1 Objectives and Corresponding Endpoints (cont.)

Exploratory Pharmacokinetic/ Pharmacodynamic Objectives	Corresponding Endpoints

 To assess the systemic PK profile of RO6867461 	
 Plasma concentration of RO6867461 at specified timepoints

 To evaluate the RO6867461, ranibizumab, free VEGF-A, and Ang-2 profile in aqueous humor 	
 Relationship between aqueous humor RO6867461 concentrations or PK parameters and free VEGF-A and Ang-2 concentrations Relationship between aqueous humor ranibizumab concentrations or PK parameters and free VEGF-A and Ang-2 concentrations Time course of free VEGF-A and Ang-2 concentrations in aqueous humor
Immunogenicity Objective	Corresponding Endpoints

 To investigate the formation of plasma anti-RO6867461 antibodies 	
 Incidence of ADAs during the study
Exploratory Biomarker Objective	Corresponding Endpoints

 To explore levels of potential biomarkers of angiogenesis and inflammation in aqueous humor at baseline and at additional timepoints to assess their response to RO6867461 	
 Relationship between aqueous humor concentration of potential biomarkers with primary and secondary endpoints

ADA = anti-drug antibody; Ang-2 = angiopoietin-2; BCVA = best corrected visual acuity; CFT = central foveal thickness; CNV = choroidal neovascularization; CST = central subfield thickness; ETDRS = Early Treatment Diabetic Retinopathy Study; FFA = fundus fluorescein angiography; IVT = intravitreal; PK = pharmacokinetic; SD-OCT = spectral domain optical coherence tomography; VEGF-A = vascular endothelial growth factor A.

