4.2.2 Masking

This is a patient- and outcome assessor (BCVA and Central Reading Center)-masked study. The intent of this design allows for a single investigator per site to be present at a given visit to fulfill the masking requirements of this study.

At a site level:

- *Patients and BCVA examiners will be masked to treatment assignment. BCVA examiners will also be masked to study eye (see Section 4.5.5.1). All other site personnel that do not have a role in drug preparation and/or treatment delivery should be masked to study eye drug assignment.*
- *The investigator administering the patient's treatment (RO6867461, comparator ranibizumab, or sham) and/or pharmacist/designated personnel responsible for drug preparation will be unmasked to treatment assignment.*

The number of unmasked study personnel should be limited to ensure the integrity of this masked study. All roles for each study staff member should be clearly documented in the site delegation log. The delegation log must be signed by the Principal Investigator. Unmasked personnel cannot switch to a masked role, but masked

personnel can switch to an unmasked role. Any change should be documented in the delegation log.

At a study level:

The Central Reading Center personnel, study vendors, and the Sponsor (with the exception of a point person[s] to support unmasked site personnel and IMC members in the case of an optional interim analysis; Section 3.1.2 and Section 6.9) and its agents will be masked to study eye drug assignment.

For biosamples:

To maintain the masked design of the study, blood samples collected at timepoints specified in the schedule of activities (Appendix 1) will also be taken from all patients receiving ranibizumab per the RO6867461 schedule. The samples from these patients may or may not be analyzed. Unmasking for independent analysis of the relevant biosamples during the conduct of the study will be performed according the Sponsor's internal standard procedures in place to ensure integrity of the data. The number of Roche representative(s) and delegates unmasked will be kept to the minimum required to address the objective of the biosample analysis.

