5.2.1 Adverse Events

According to the ICH guideline for Good Clinical Practice, an adverse event is any untoward medical occurrence in a clinical investigation subject administered a pharmaceutical product, regardless of causal attribution. An adverse event can therefore be any of the following:

- Any unfavorable and unintended sign (including an abnormal laboratory finding), symptom, or disease temporally associated with the use of a medicinal product, whether or not considered related to the medicinal product
- Any new disease or exacerbation of an existing disease (a worsening in the character, frequency, or severity of a known condition), except as described in Section [5.3.5.9](#)
- Recurrence of an intermittent medical condition (e.g., headache) not present at baseline
- Any deterioration in a laboratory value or other clinical test (e.g., ECG, X-ray) that is associated with symptoms or leads to a change in study treatment or concomitant treatment or discontinuation from study drug
- Adverse events that are related to a protocol-mandated intervention, including those that occur prior to assignment of study treatment (e.g., screening invasive procedures such as biopsies)

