5.2.3 Adverse Events of Special Interest (Immediately Reportable to the Sponsor)

Non-serious or serious adverse events of special interest are required to be reported by the investigator to the Sponsor immediately (i.e., no more than 24 hours after learning of the event; see Section 5.4.2 for reporting instructions). Adverse events of special interest for this study include the following:

- Cases of potential drug-induced liver injury that include an elevated ALT or AST in combination with either an elevated bilirubin or clinical jaundice, as defined by Hy's law (see Section 5.3.5.6)
- Suspected transmission of an infectious agent by the study drug, as defined below

Any organism, virus, or infectious particle (e.g., prion protein transmitting transmissible spongiform encephalopathy), pathogenic or non-pathogenic, is considered an infectious agent. A transmission of an infectious agent may be suspected from clinical symptoms or laboratory findings that indicate an infection in a patient exposed to a medicinal product. This term applies only when a contamination of the study drug is suspected.

- Sight-threatening adverse events

An adverse event *is* considered to be sight threatening *and* should be reported by the investigator to the Sponsor immediately (i.e., no more than 24 hours after learning of the event; or reporting instructions) if it meets one or more of the following criteria:

- It causes a decrease of ≥ 30 letters in BCVA (compared with the last assessment of VA prior to the most recent treatment) lasting more than 1 hour
- It requires surgical intervention (i.e., conventional surgery, vitreous tap, or biopsy with IVT injection of anti-infectives, or laser or retinal cryopexy with gas) to prevent permanent loss of sight

- It is associated with severe intraocular inflammation (i.e., 4+ anterior chamber cell/flare or 4+ vitritis; see the definitions of intraocular inflammation in Section 5.3.5 and grading scales for assessment in Appendix 2)
- In the opinion of the investigator, it may require medical intervention to prevent permanent loss of sight

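### Whether study-eye vision loss attributed to AMD enters the adverse event data rests on an undefined judgment of expectedness by an investigator who may know the arm

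*Combined protocol and SAP*

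**What the plan says.** - **Definition of an adverse event (Section 5.2.1).** New disease is on the list, and so is "exacerbation of an existing disease (a worsening in the character, frequency, or severity of a known condition), except as described in Section"; the section it points to is 5.3.5.9.
- **AMD deterioration (Section 5.3.5.9).** Deterioration of a kind foreseen in AMD "should be recorded as an adverse event if judged by the investigator to have unexpectedly worsened in severity or frequency", or to have changed in nature. Neither this section nor any other defines *unexpectedly*.
- **Special-interest events (Section 5.2.3).** One category is "Sight-threatening adverse events". An adverse event belongs to it if, among other criteria, "It causes a decrease of ≥ 30 letters in BCVA" against the last acuity before the most recent treatment, for more than 1 hour. Other criteria are surgery to save sight, severe inflammation, and "In the opinion of the investigator, it may require medical intervention to prevent permanent loss of sight". The category is not limited to the study eye. Section 5.4 requires reporting within 24 hours.
- **Masking (Section 4.2.2).** "The intent of this design allows for a single investigator per site to be present at a given visit", and the investigator who gives the treatment is unmasked. Section 5.3 leaves the assessment of adverse events to the investigator and names no masked assessor.
- **Endpoint and analysis.** Table 1 lists "Incidence and severity of ocular adverse events" under the safety objective. Section 6.6 summarizes ocular events by eye, with patients grouped by treatment received. It names no table of special-interest events or of letter loss.
- **Acuity data.** BCVA is measured by a masked examiner (Section 4.5.5.1) at every scheduled visit (Appendix 1). The secondary endpoints include the proportions avoiding losses of up to 15 letters, counted from baseline.

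**The concern.** The safety objective is to evaluate RO6867461 at 12- and 16-week intervals, and Section 1.3 itself names under-treatment as the risk that the Week 24 switch in Arm B is meant to limit. Under-treatment would show as AMD deterioration in the study eye. That is the one kind of ocular worsening that the plan removes from the ordinary adverse event rule and makes conditional on a judgment of expectedness.

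If that judgment is made by someone who knows the arm, the ocular adverse event summaries may differ between arms for the same clinical course. A large loss could also stay outside the special-interest data and the 24-hour route, because both require an adverse event first.

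**Working it through.** **1. How the sections fit together.**

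| Step | Section | Condition |
|---|---|---|
| Is it an adverse event? | 5.2.1 | Worsening of a known disease counts, with AMD excepted to 5.3.5.9 |
| AMD worsening | 5.3.5.9 | Recorded if judged unexpected or changed in nature |
| Is it sight-threatening? | 5.2.3 | An adverse event that meets a criterion, such as a fall of ≥30 letters |
| 24-hour report? | 5.4 | Serious or special-interest adverse events |

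Each step presupposes the one above it. A fall of ≥30 letters attributed to AMD and judged expected stops at the second row. The serious-event route is no way round, because Section 5.2.2 also starts from an adverse event. For comparison, Section 5.3.5.8 has other preexisting conditions recorded on worsening alone, and Section 4.6.2 attaches a third condition to a ≥30-letter drop: that it be considered adverse and related to study treatment.

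**2. Who decides.** The decision is the investigator's. The investigator who injects is unmasked, and the design needs only one at a visit. The person judging expectedness can therefore know the arm.

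**3. What the BCVA endpoints show instead.** They count from baseline, and their largest loss category is 15 letters. Take an eye that gains 16 letters in the initial phase and then falls 30. Its change from baseline is 16 − 30 = −14. It counts as a loss of ≥10 letters, but still as avoiding a loss of ≥15, and nothing shows a fall of 30.

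**4. The reference visit.** Section 5.2.3 measures the fall from before the most recent treatment. Section 4.3.2.1 includes sham among the study treatments. If sham counts, the reference is about 4 weeks back in every arm. If only active injections count, it is 4 weeks back in Arm C but up to 12 in Arm A and 16 in Arm B. A table that uses this reference must say which is meant.

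**5. Size, by assumption.** The plan's one precision figure reproduces: 1.2816 × 13.5 × √(1/30 + 1/15) = 1.2816 × 4.269 = 5.47, stated as 5.5 letters in Section 6.1. It confirms arms of 30 and 15; the point does not depend on it.

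The documents give no rate of AMD deterioration under these regimens and no recording probability. Suppose the same true share *r* in one RO6867461 arm (n = 30) and in ranibizumab (n = 15), with recording probabilities *a* and *b*. The spurious gap is *r* × |*a* − *b*|. The standard error of a difference at the common true share is √[*r*(1 − *r*)(1/30 + 1/15)].

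| True share | Gap, 100% vs 50% recorded | Gap, 80% vs 60% | SE | First gap ÷ SE |
|---|---|---|---|---|
| 5% | 2.5 points | 1 point | 6.9 points | 0.36 |
| 10% | 5 points | 2 points | 9.5 points | 0.53 |
| 20% | 10 points | 4 points | 12.6 points | 0.79 |

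With equal recording every gap is zero, and exchanging *a* and *b* reverses its sign. At a true share of 20%, the expected true counts of 6 and 3 become 6 and 1.5, or 3 and 3.

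These shares concern deterioration of any size. Falls of ≥30 letters would be rarer: at an assumed 1% to 3%, 30 × 0.01 to 30 × 0.03 gives 0.3 to 0.9 patients in an arm of 30. One unrecorded case can then decide whether an arm shows zero.

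**The case against.** **A contradiction between sections?** A reader might infer that Section 5.2.3 makes any 30-letter loss a sight-threatening event, whatever its cause, and so conflicts with Section 5.3.5.9. The text does not support this. Section 5.2.3 classifies adverse events, and Section 5.2.1 expressly makes way for Section 5.3.5.9. The sections are nested. What is missing is a statement on how a large loss attributed to AMD is to be handled.

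**A bias toward RO6867461?** A reader might also infer that recurrence late in a 12- or 16-week interval is easier to call expected than recurrence on monthly ranibizumab, so that the longer intervals look safer. This is plausible but not documented. Section 5.3.5.9 ties expectation to the disease, not the regimen. Section 1.3 expects less frequent dosing, on average, at least to hold the initial gains. An unmasked investigator could equally over-record on an investigational drug. If sham visits set the reference, slow recurrence would also seldom produce a 30-letter fall within 4 weeks.

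**Already visible?** Masked BCVA is analysed by arm over time, so much of any vision loss will be seen. That stands, and it limits the harm to the adverse event and special-interest data. It does not cover a fall from an improved score, or the ≥30-letter category.

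**Small numbers.** The illustrative gaps are all below one standard error, in an estimation study whose adverse events are only summarized. That also stands. The case rests on rare, serious losses and on a clear recording rule, not on a demonstrated shift in rates.

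**Conclusion.** The point holds in limited form. A study-eye vision loss attributed to AMD, including one of ≥30 letters, becomes an adverse event only if the investigator finds it unexpected or changed in nature. That test is undefined, and the person applying it may know the arm. Recording can therefore differ by arm for the same loss.

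That it will differ is not shown, and neither direction nor size can be determined from the documents. The gaps of 1 to 10 percentage points rest wholly on assumed true shares of 5% to 20% and on assumed unequal recording. The masked BCVA endpoints are unaffected and show much of the loss, though from baseline and without a ≥30-letter category. This is a cheap improvement, not a flaw that threatens the primary analysis.

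**What to change.** 1. **Section 5.3.5.9.** State that study-eye AMD deterioration meeting the ≥30-letter criterion of Section 5.2.3 (with its reference visit and its duration of more than 1 hour), or its surgical-intervention criterion, is recorded as an adverse event and reported as one of special interest, whether or not it was anticipated.
2. **Section 6.6.** Add a by-arm table, programmed from the masked BCVA data, of study eyes with a fall of ≥15 and of ≥30 letters at any scheduled visit. Use references that are the same in all arms: the previous scheduled 4-weekly visit, with sham visits counted as treatment visits, and also the best previous score.
3. **Section 4.6.2.** Its condition that a ≥30-letter drop be considered adverse and related must be reconciled with Sections 5.2.3 and 5.3.5.9, because the first change bears on the word *adverse* there. No stopping rule is proposed here.

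The cost is one sentence, one table from data already collected, and a check of wording. The downside is a few more reported events, and some AMD progression will appear in both the efficacy and the safety outputs.
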